3.2 Randomisation

Patients with septic shock fulfilling the inclusion criteria will be randomised if they do not fulfil an exclusion criterion. The 1:1 randomisation will be centralised and web-based according to the computer-generated allocation sequence list, stratification variables (haematological or metastatic cancer (Y/N) and trial site), and varying block size at Copenhagen Trial Unit (CTU). The allocation sequence list will exclusively be known to the data manager at CTU and will be unknown to the investigators to allow immediate and concealed allocation to one of the two intervention groups. Each participant will be allocated a unique patient-screening number.

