9.2.2 Timing

All variables are defined in Appendix 2.

Baseline variables:

- Sex
- Date of birth

The CLASSIC trial protocol Page 28/82

- Date of admission to hospital
- Date and time of admission to ICU
- From where was the participant admitted to ICU
 - o Emergency department or directly from the pre-hospital setting
 - Hospital ward
 - Operating or recovery room
 - Another ICU
- Focus of infection:
 - o Pneumonia
 - o Gastrointestinal infection
 - Urinary tract infection
 - Skin or soft tissue infection
 - Other
- Co-morbidities:
 - o Active hematologic cancer
 - History of metastatic carcinoma
 - History of ischemic heart disease or heart failure
 - History of chronic hypertension
 - o Chronic dialysis
- Blood values, interventions and vital parameters:
 - Participant weight
 - o Highest plasma lactate value within the last 3 hours of randomisation
 - Highest dose of noradrenaline within the last 3 hours of randomisation
 - o Volumes of IV fluid within the last 24 hours of randomisation
 - o Use of systemic corticosteroids in the last 24 hours of randomisation
 - Highest plasma creatinine value within the last 24 hours of randomisation
 - Use of acute renal replacement therapy in the last 3 days prior to randomisation
 - Habitual plasma creatinine value prior to current hospitalisation (mark estimated or measured)
- Values for the Simplified Mortality Score (SMS score)[43] at ICU admission not covered by the above:
 - Lowest measured systolic blood pressure in the last 24 hours prior to randomisation
 - Respiratory support within the last 24 hours of randomisation (support during surgery excluded)

Daily during ICU admission (day form):

- Fluid input and output
 - Total volume and specific type of IV isotonic crystalloids (isotonic saline and buffered solutions: Ringer's lactate, Ringer's acetate and PlasmaLyte™)
 - o Total volume of other IV fluids
 - Total volume of albumin
 - Total volume of fluids with medications
 - Total volume of fluids with nutrition
 - Total volume of blood products

The CLASSIC trial protocol Page 29/82

- Urinary output on this day (ml)
- Total volume of other losses on this day including drainage, aspirates, stools and bleeding
- Did a major protocol violation occur on this day?
- Use of infusion of vasopressor or inotrope on this day
- Use of systemic corticosteroids on this day
- Use of mechanical ventilation on this day
- Use of renal replacement therapy on this day
- Plasma concentration of creatinine

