10.1 Sample size and power

10.1.1 Sample size estimation

By enrolling 1554 (2 x 777) participants, we can show a 15% relative risk reduction (7% absolute) in the restrictive group from an estimated 45% 90-day mortality in the standard care group (data from our previous CLASSIC pilot, TRISS and 6S trials [2, 3, 5], systematic reviews [23, 44] and a recent large cohort study [4]) at type 1 and 2 error levels of 5% and 20% (power=80%), respectively.

The CLASSIC trial protocol Page 31/82

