 - O Highest dose of noradrenaline within the last 3 hours of randomisation: highest infusion rate in μg/kg/minVolumes of IV fluid within the last 24 hours of randomisation: all crystalloids (any saline, NaHCO3-, Ringer's and Plasmalyte™ solutions), colloids (albumin 4, 5 or 20%, gelatine, hydroxyethyl starch and dextran solutions) and blood products (units of red cells, plasma or platelets) the participant has received within the last 24-hours independent of location (in- or pre-hospital) including fluids with IV medication and IV nutrition. Intraosseous fluid will be counted as IV

0

 Use of systemic (IV, IM or oral/per GI tube) corticosteroids in the last 24 hours of randomisation including any dose of hydrocortisone, methylprednisolone, dexamethasone or prednisolone

The CLASSIC trial protocol

- Highest plasma creatinine value within the last 24 hours of randomisation: in μmol/L
- Use of acute renal replacement therapy in the last 3 days prior to randomisation: any form
 of renal replacement therapy (e.g. dialysis, hemofiltration or hemo-diafiltration) at any rate
 in the last 72 hours, which has been initiated during the current hospitalisation (including
 any stay in another hospital immediately prior that in the site)
- \circ Habitual plasma creatinine value prior to current hospitalisation: estimated or measured in μ mol/L. If no there are no values recorded in source data, we will estimate habitual plasma creatinine

-The simplified mortality score (Appendix 6) is based on 7 variables obtained in the 24 h prior to randomisation of a patient into the trial [43]. The variables include:

- o Age: defined in inclusion criteria
- Lowest systolic blood pressure: either invasive or non-invasive in mmHg. In case of cardiac arrest within the 24-h period '0' will be registered.
- Acute surgical admission: Surgery during current hospital admission that was added to the operating room schedule.
- o Hematologic malignancy or metastatic cancer: Defined in the stratification variables.
- Vasopressors/inotropes: Use of continuous infusion of vasopressor or inotrope (defined in the inclusion criteria).
- Respiratory support: Use of invasive or non-invasive mechanical ventilation including continuous mask CPAP or CPAP via tracheostomy within the last 24 hours prior to randomisation. Intermittent CPAP and high flow nasal cannula oxygen therapy are NOT considered as respiratory support

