- Renal replacement therapy: Use of acute or chronic intermittent or continuous renal replacement therapy.

Definition of daily collected variables:

- -Fluid input and output in mL cumulated from the 24-h ICU charts
 - Total volume and specific type of IV isotonic crystalloids: isotonic saline and buffered solutions: Ringer's lactate, Ringer's acetate and PlasmaLyte™
 - o Total volume of other IV fluids: e.g. <10% glucose, glucose-potassium, sodium-potassium-chloride, half-saline
 - Total volume of albumin (4, 5 or 20% solutions combined)
 - o Total volume of fluids with medications: both parenteral and enteral
 - Total volume of fluids with enteral and parenteral nutrition: e.g. enteral nutrition solutions and >10% glucose, protein or lipid solutions given parenterally or enterally
 - o Total volume of non-nutritional enteral/oral fluids: e.g. water or soft drinks
 - o Total volume of blood products: defined in inclusion criteria
 - Urinary output on this day
 - o Any fluid volume removed during renal replacement therapy
 - Total volume of other losses on this day including drainage, aspirates, stools and bleeding

-Major protocol violation on this day:

The CLASSIC trial protocol Page 48/82

- \circ Restrictive group: IV fluids given without one of the extenuating circumstances occurring on this day (y/n)
- Standard care group: the violations (no IV fluid given) will be assessed from all the day form registrations regarding fluid input at the end of trial for each participant
- -Use of infusion of vasopressor or inotrope on this day: defined in the inclusion criteria
- Use of systemic corticosteroids on this day: defined in the baseline data
- -Use of mechanical ventilation on this day: invasive mechanical ventilation as the use of positive pressure ventilation using a ventilator via a cuffed tube (oral, nasal or tracheostomy). CPAP is NOT mechanical ventilation.
- -Use of renal replacement therapy on this day: any form of renal replacement therapy (e.g. dialysis, hemofiltration or hemo-diafiltration) at any rate on this day.
- -Plasma concentration of creatinine in µmol/L on this day

Definition of outcome measures

Primary outcome:

90 day mortality: death from any cause within 90 days post-randomisation.

Secondary outcomes:

- -Serious adverse events as at least one episode of either the following observed in the ICU:
 - Ischemic events defined as either
 - o Cerebral ischemia defined as any form of cerebral ischemia on a CT- OR MRI scan

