 - Acute myocardial ischemia defined as participant with acute myocardial infarction (STelevation myocardial infarction or non-ST elevation myocardial infarction) or unstable
 angina pectoris according to the criteria in the clinical setting in question (e.g. elevated
 biomarkers, ischemic signs on ECG and clinical presentation) AND the participant
 received treatment as a consequence of this (reperfusion strategies (PCI/thrombolysis)
 OR initiation/increased antithrombotic treatment).
 - Intestinal ischemia defined as ischemia verified by endoscopy OR open surgery OR CTangiography.
 - Limb ischemia defined as clinical signs AND need of open/percutaneous vascular intervention, amputation OR initiation/increased antithrombotic treatment.
 - A new episode of severe acute kidney injury defined as modified KDIGO3 [41]: a 3.0 times increase in baseline p-creatinine, or increase in p-creatinine to ≥354 μmol/L, or use of renal replacement therapy (any form) in participants who did not receive this before randomisation.
- -Serious adverse reactions: total number of SARs and number of SARs per participant in the ICU. Serious adverse reactions are defined below.

The CLASSIC trial protocol Page 49/82

- -Number of days alive without life support at day 90: will be assessed from the use of life support including vasopressor/inotrope, mechanical ventilation and renal replacement therapy as defined in the inclusion criteria, baseline and daily variables. Total number of days alive without all of the 3 life supporting interventions within 90 days after randomisation.
- -Days alive and out of hospital at day 90: will be assessed from the discharge date from the index hospitalisation, the number of days readmitted to hospital (if any) and date of death, if relevant, within the 90-day period
- -1-year mortality: landmark mortality 1-year post-randomisation. If the participant has deceased, date of death will be registered.

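### The kidney component of the SAE outcome is meant to capture new severe AKI, but its creatinine criteria do not exclude participants who already met them at randomisation

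*Protocol*

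**What the plan says.** Protocol section 7.2 makes the SAE composite a secondary outcome: ischaemic events in four territories, or severe AKI. The word *new* is attached to the AKI part only. Appendix 2 (section 14.2) gives the operational definition: "A new episode of severe acute kidney injury defined as modified KDIGO3 [41]: a 3.0 times increase in baseline p-creatinine", or an increase to at least 354 µmol/L, or any RRT "in participants who did not receive this before randomisation". The SAP repeats the outcome and refers to the protocol for definitions.

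Two creatinine values are recorded before the trial intervention starts: "Habitual plasma creatinine value prior to current hospitalisation", which may be measured or estimated, and "Highest plasma creatinine value within the last 24 hours of randomisation". Chronic dialysis and acute RRT in the preceding 3 days are also recorded.

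The day form in section 9.2.2 has yes/no SAE items for the four ischaemic events. It has none for AKI; it records creatinine and RRT for each day.

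The SAP appendix on subgroups stages AKI at randomisation, with stage 2 as 2.0 to 2.9 times baseline and stage 3 as 3.0 times baseline, the 354 threshold or start of RRT.

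**The concern.** The label and the criteria do not match. Of the three ways to meet the kidney component, only RRT excludes people who were already there. The two creatinine criteria do not, and the reference value for the first of them is not named in Appendix 2.

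Because the day form has no AKI item, the component has to be derived from daily creatinine and RRT. No derivation rule says how a new episode is recognised. Applied literally, the criteria count a participant who arrives at stage 3 as an event.

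Severe AKI that was present before allocation cannot have been caused by the allocated fluid strategy. Counting it adds the same events to both arms and makes a real effect on SAEs, in either direction, look smaller than it is.

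**Working it through.** **1. The three criteria side by side**

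| Criterion | Reference value named? | Excludes those already positive? |
|---|---|---|
| 3.0 times baseline creatinine | No | No |
| Creatinine 354 µmol/L or more | Not needed | No |
| RRT | Not needed | Yes |

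A participant on chronic dialysis is therefore kept out by the third row but can still enter through the second.

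**2. What baseline must mean**

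The SAP measures AKI present at randomisation as a multiple of baseline. That is possible only if baseline precedes the acute illness, so it points to habitual creatinine.

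The other candidate, the 24-hour peak, works poorly. Take habitual 80, 200 at randomisation, and a later peak of 300 µmol/L. The ratio to habitual is 300/80 = 3.75, but the ratio to the 24-hour peak is 300/200 = 1.5, and 300 is below 354. No criterion is met despite clear progression. On that reading the 3.0-fold criterion would also be redundant for any 24-hour peak above 354/3.0 = 118 µmol/L, because 354 would be reached first.

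With habitual creatinine as baseline, a participant with habitual 80 has a threshold of 3.0 × 80 = 240. If the 24-hour peak was 300 and the first day form still shows 240 or more, an event is scored on day 1 although stage 3 was present before allocation.

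**3. The plan's own figures**

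Inputs: "By enrolling 1554 (2 x 777) participants" (section 10.1.1); "The 1:1 randomisation will be centralised and web-based" (section 3.2); SAE control rate 25%, 15% relative risk reduction (RRR), type 1 error 1% (section 10.1.2); two-tailed tests (section 10.2).

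Calibration: the primary outcome, 45% v 38% at 5% and 80% power, gives 777 per arm, as stated.

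SAE power, with p1 = 0.25, p2 = 0.85 × 0.25 = 0.2125, mean 0.23125:

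- Standard error under no difference: √(2 × 0.23125 × 0.76875/777) = 0.02139
- Standard error under the alternative: √((0.25 × 0.75 + 0.2125 × 0.7875)/777) = 0.02137
- Power = Φ[(0.0375 − 2.576 × 0.02139)/0.02137] = Φ(−0.82) = 20.5%

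The plan states 50%, which these inputs do not reproduce. That is a separate matter; 20.5% is the undiluted reference here.

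**4. Dilution**

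Let f be the share of the planned 25% control rate that was already present, equal in both arms and unaffected by treatment. The true risk ratio for new events is 0.85.

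Observed risk ratio = f + (1 − f) × 0.85, so observed RRR = 0.15 × (1 − f).

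The documents give no value for f; those below are assumptions.

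| f | Already present (points of the 25%) | Observed RR | Observed RRR | Power, all counted | Power, new events only |
|---|---|---|---|---|---|
| 0 | 0 | 0.85 | 15% | 20.5% | 20.5% |
| 20% | 5 | 0.88 | 12% | 11.9% | 14.6% |
| 40% | 10 | 0.91 | 9% | 6.2% | 9.8% |

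The last column keeps all 777 per arm in the denominator, with control rates of 20% and 15%. Counting new events only restores the ratio of 0.85 and gains some power even though there are fewer events. When there is no true effect the observed ratio stays at 1 for any f.

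**The case against.** **The text omits a rule; it does not say that existing disease counts.** The phrase about a new episode heads all three criteria, and both creatinine criteria speak of an increase. This is fair as to intent. It does not tell a programmer what to do with a participant already over the threshold, and the protocol supplied the exclusion for RRT only.

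**Components are reported separately.** True, but the kidney component carries these cases itself and would be diluted more than the composite.

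**Balance is assumed.** Whether creatinine is still above threshold on the first day form may itself depend on allocation. This stands as a limit on the claim of pure dilution.

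**Stronger readings.** Three are tempting and are not supported:

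- *All the ischaemic criteria also count old disease.* The documents do not call ischaemia new, and section 8.1 confines adverse events to those arising during the trial. The cardiac criterion requires an acute, treated event; the limb criterion requires intervention, amputation or started or increased treatment. Only "Cerebral ischemia defined as any form of cerebral ischemia on a CT- OR MRI scan" and "Intestinal ischemia defined as ischemia verified by endoscopy OR open surgery OR CTangiography" lack wording on onset, and that is a drafting matter.
- *This is the trial's main harm comparison.* SAEs are one of seven secondary outcomes. The monitoring committee sees them at the third interim analysis, but the stopping boundary names the primary outcome, SARs and SUSARs.
- *The dilution could halve the effect.* Adding cases on top of 25% gives an apparent reduction of 7.5% if 20% of participants are already positive. That needs a control SAE rate of 0.20 + 0.80 × 0.25 = 40%, against the planned 25%. The planned subgroup of stage 2 or above shows that AKI at entry is expected, not how much of it is stage 3.

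**Conclusion.** The point holds for the kidney component. Its criteria, applied as written with baseline read as the SAP uses it, count severe AKI already present at randomisation as a new episode. The likely consequence is a weaker SAE comparison, not a false finding.

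The size cannot be derived from the documents. The range of 12% to 9% in place of a true 15% rests on three assumptions: that 20% to 40% of the planned event rate is already present, that these cases are balanced, and that treatment does not affect whether they are counted. The contradiction between label and rule does not depend on those assumptions.

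**What to change.** In Appendix 2:

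- Define baseline creatinine as the habitual value.
- Count the two creatinine criteria only in participants who did not already meet modified KDIGO3 on the highest creatinine in the 24 hours before randomisation and who are not on chronic dialysis.
- Let those already at stage 3 without RRT qualify only through the existing RRT criterion.
- Report per arm how many were at stage 3 at randomisation.
- Present the definition as now worded as a sensitivity analysis.

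As a minor wording point, add to the cerebral and intestinal definitions that the event must follow randomisation, as all six SAR definitions already do.

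The kidney change needs no new data: both creatinine values, chronic dialysis and prior acute RRT are collected, so it can be applied at analysis. The SAP's list of changes dates the final analyses to March 2022; if the outcome has already been derived, the revised rule should be reported as specified afterwards.

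The costs are a lower event rate, no credit for further creatinine worsening in those already at stage 3 unless RRT starts, and some misclassification where habitual creatinine was estimated. The baseline form marks which values are estimated, so the last can be described.

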10.2.4 Accountability procedure for missing data/population for analysis

If less than 5% of data are missing for any primary or secondary outcome, a complete case analysis without imputation of missing values will be performed. If missing data are more than 5%, a statistician masked for the intervention will assess whether data are 'missing completely at random' (MCAR criterion) based on a rational assessment of the pattern of missing data [48]. Little's test will be used if doubt remains [49]. If it is concluded that data are not MCAR, multiple imputation using chained equations will be performed by creating 10 input datasets under the assumption that the data are 'missing at random' (MAR criterion) [50, 51]. We will use outcomes and the most important baseline characteristics in the multiple imputations as will be outlined in the detailed statistical analysis plan.

If multiple imputations are used, then the primary result of the trial will be based on these data. The unadjusted, non-imputed analysis will also be presented. If multiple imputation is used because of missing outcome data, we will use a best-worst worst-best case scenario as a sensitivity analysis to assess the potential impact of any pattern of missingness including that the data are 'missing not at random' (MNAR criterion). In the 'best-worst-case' scenario it is assumed that all participants lost to follow-up in the experimental group have had a beneficial outcome (e.g. have survived, had no SAE etc.); and all those with missing outcomes in the control group have had a harmful outcome (e.g. have not survived; have had a SAE etc.). Conversely, in the 'worst-best-case' scenario, it is assumed that all participants who were lost to follow up in the experimental group have had a harmful outcome; and that all those lost to follow-up in the control group have had a beneficial outcome. When continuous outcomes are used, a 'beneficial outcome' will be defined as the group mean plus two SD of the group mean or highest possible value whichever is smallest, and a 'harmful outcome' will be defined as the group mean minus two SD of the group mean or lowest possible value whichever is highest.

11 Quality control and quality assurance

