- -HRQoL at 1-year (+/- 2 weeks): EQ-5D-5L and EQ-VAS scores (https://euroqol.org/) obtained by survey by mail or phone as chosen by the participant. Non-survivors will be given the worst possible score. If the participant is incapable of answering the questionnaire (e.g. due to cognitive impairment or coma) we will ask proxies to assess HRQoL for the trial participant (proxy point of view) using the questionnaire aimed for proxies. Non-survivors will be given the worst possible score. EQ-5D-5L will be converted to an index value in combination with the EQ-VAS quantitative measure (0-100 points) quantifying self-rated health
- -Cognitive function at 1-year (+/- 2 weeks): the Montreal Cognitive assessment (MoCa) MINI score (or '5-miniute protocol') using the translations of the MoCa full v. 7.1 (http://www.mocatest.org/). The score will be obtained in all survivors by interview as this was recommended to be the test of cognition in a core outcome set for patients with acute respiratory failure following a modified Delphi process involving patients, researchers and clinicians from multiple continents (http://www.improvelto.com/). Non-survivors will be given the worst possible score. The cognitive function score will be conducted before HRQoL to ensure an equal procedure and avoid that patients are disturbed or tired from the HRQoL score.

If the MoCa MINI, which is validated for phone interview [52], has not been released at the time of the first assessment (1-year after randomisation of the first patient), we will adapt the MoCa MINI from the MoCa full v. 7.1.

SARs will be defined as follows:

- -General tonic-clonic seizures: stiffening and/or jerking movements of all 4 extremities in a patient who becomes or is unconscious in the ICU after randomisation
- -Anaphylactic reactions defined as urticarial skin reaction **AND** at least one of the following observed in the ICU after randomisation
 - Worsened circulation (>20% decrease in blood pressure or >20% increase in vasopressor dose)
 - Increased airway resistance (>20% increase in the peak pressure on the ventilation)
 - Clinical stridor or bronchospasm
 - o Subsequent treatment with bronchodilators

The CLASSIC trial protocol Page 50/82

- -Central pontine myelinolysis seen on CT or MRI scan within the 90-day period after randomisation
- -Hypernatremia defined as p-Na > 159 mmol/L on any plasma sample, including point-of-care testing, done in the ICU after randomisation

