The trial intervention is not blinded for investigators, clinical staff and patients, as blinding of IV fluid restriction versus standard care is not feasible. The statistician assessing all outcomes will be masked for the allocation. The data for 90-day and 1-year mortality will be collected from electronic patient records or central national registries in most participating countries. The remaining outcomes will be provided by local investigators, who are not blinded for the intervention, by entering data from patients' files. The management committee will write the preliminary abstract with the group allocation masked; this abstract will be published as a supplement to the primary trial report.^{5,6}

Outcome measures

Primary outcome measure

The primary outcome measure is all-cause mortality at day 90 after randomisation.

Secondary outcome measures

We have 7 secondary outcome measures:

 Number of participants with one or more serious adverse events (SAEs) in the ICU defined as ischaemic events (cerebral, cardiac, intestinal or limb ischaemia) or a new episode of severe AKI (modified KDIGO3⁷)

- Number of participants with one or more serious adverse reactions (SARs) to IV crystalloids in the ICU
- Days alive at day 90 without life support (vasopressor / inotropic support, invasive mechanical ventilation or renal replacement therapy (RRT))
- Days alive and out of hospital until day 90
- All-cause mortality at 1 year after randomisation
- Health-related quality of life (HRQoL) 1 year after randomisation measured using the EuroQoL EQ-5D-5L scores ⁸
- Cognitive function 1 year after randomisation as assessed by the telephone MINI-Montreal Cognitive Assessment (MINI-MoCA) score ⁹

Detailed definitions of the outcome measures are available in the protocol.

Missing data

If less than 5% of data required for any specific analysis on primary or secondary outcomes are missing, a complete case analysis will be performed. If more than 5% are missing, and it is concluded that data are not 'missing completely at random' (MCAR criterion),^{10,11} multiple imputation using chained equations will be performed by creating 25 input datasets under the assumption that the data are 'missing at random' (MAR criterion).^{12,13}

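### The cognitive outcome has no scoring rule for survivors too impaired to be tested, so they fall into the ordinary missing-data rules although their scores are missing because cognition is poor

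*Protocol*

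**What the plan says.** Protocol Appendix 2 (outcome definitions) makes the 1-year cognitive score an interview measure: "The score will be obtained in all survivors by interview". For deaths it adds: "Non-survivors will be given the worst possible score". No proxy and no assigned score is given for a living participant who cannot be interviewed.

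The HRQoL definition just before it does foresee that participant: "If the participant is incapable of answering the questionnaire (e.g. due to cognitive impairment or coma) we will ask proxies to assess HRQoL".

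The SAP names the instrument ("Cognitive function 1 year after randomisation as assessed by the telephone MINI-Montreal Cognitive Assessment (MINI-MoCA) score"), refers to the protocol for definitions and adds no scoring rule. The 1-year form in Protocol 9.2.2 collects death, EQ-5D-5L and EQ-VAS, and MoCa scores; it lists no reason for a missing test.

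The missing-data rules are general. The SAP (Missing data) says: "If less than 5% of data required for any specific analysis on primary or secondary outcomes are missing, a complete case analysis will be performed". Protocol 10.2.4 agrees: "a complete case analysis without imputation of missing values will be performed". Above 5%, and if the data are judged not missing completely at random, the SAP states that "multiple imputation using chained equations will be performed by creating 25 input datasets", assuming data missing at random, separately by arm, using baseline variables and the relevant outcomes. Best-worst and worst-best scenarios follow only if multiple imputation is used.

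**The concern.** A survivor in coma, or too impaired to be interviewed, lacks a score because of the very thing being measured. The plan recognises that such survivors may exist, since it arranges a proxy for their HRQoL, and it accepts a worst score for death. On cognition, a participant who dies counts at the bottom of the scale, while one who is alive but untestable has no score. The default is omission, or imputation from participants who could be tested. Neither route encodes why the score is absent.

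If restriction changes the number of survivors left in that state, part of the effect on cognition falls outside the outcome meant to capture it, and below the 5% threshold no sensitivity analysis would show it.

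**Working it through.** The documents state no figure for the cognitive outcome, so there is none to reproduce. Two things can be checked: when the safeguards start, and how much the handling can move the comparison.

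**1. When imputation and the scenarios start**

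Inputs: 777 per arm (Protocol 10.1.1); 1-year mortality 55% in control and a 15% relative reduction (Protocol 10.1.2), so 0.55 × 0.85 = 46.75% in the restrictive arm.

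- Survivors: 777 × 0.45 + 777 × 0.5325 = 349.65 + 413.75 = 763.4.
- 5% of all participants: 0.05 × 1554 = 77.7.
- As a share of survivors: 77.7 / 763.4 = 10.2%.

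So if deaths count as observed scores and no other test is missing, about one survivor in ten could be untestable and the plan would still use complete cases with no further analysis. If the 5% were instead counted among survivors only, the limit would be 0.05 × 763.4 = 38 people. The documents do not say which applies.

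**2. What the scenarios cover once they run**

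In best-worst, missing scores are set to a beneficial value in the restrictive arm and a harmful value in control; worst-best is the reverse. No scenario gives the harmful value to both arms, which is what survivors untestable through impairment would call for.

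**3. Effect on the comparison**

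Assumptions, none of them from the documents: testable survivors average 22 points, deaths score 0, and nothing else is missing. With mortality d and untestable share u among survivors:

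- worst-score mean = (1 − d)(1 − u) × 22
- complete-case mean = worst-score mean / [1 − (1 − d)u]

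*Unequal rates, 50% mortality in both arms, 3% versus 8% untestable.* Overall missingness is (0.5 × 0.03 + 0.5 × 0.08) / 2 = 2.75%, so complete case applies.

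- Worst score: 0.5 × 0.97 × 22 = 10.67; 0.5 × 0.92 × 22 = 10.12; difference 0.55.
- Complete case: 10.67 / 0.985 = 10.83; 10.12 / 0.96 = 10.54; difference 0.29.

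*Planned mortality (55% and 46.75%), restrictive minus control:*

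| Untestable, control / restrictive | Overall missing | Worst-score means (control, restrictive) | Difference | Complete-case means (control, restrictive) | Difference |
|---|---|---|---|---|---|
| 10% / 10% | 4.9% | 8.91, 10.54 | 1.63 | 9.33, 11.14 | 1.81 |
| 2% / 10% | 3.1% | 9.70, 10.54 | 0.84 | 9.79, 11.14 | 1.35 |
| 10% / 2% | 2.8% | 8.91, 11.48 | 2.57 | 9.33, 11.60 | 2.27 |

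With equal rates of 10%, the levels rise by about 0.4 and 0.6 points and the difference by 0.17. With unequal rates, complete case overstates the difference in one direction and understates it in the other. All three rows lie below 5% missing.

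These are means. The SAP's analysis may be a Poisson or negative binomial model or a Van Elteren test, so the table shows the mechanism and does not forecast the reported estimate.

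**The case against.** Several points on the other side stand.

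- A reader might infer that the worst outcomes are simply replaced by average ones. That goes too far. The imputation model uses all relevant outcomes, which may include the proxy HRQoL collected for these same survivors, so imputed values could fall below average. They still derive from participants with scores.
- A reader might infer that a real difference would be hidden. In the 3% versus 8% case it is attenuated from 0.55 to 0.29. It would reach zero only if imputation were triggered and filled every gap as for a typical testable survivor (11.00 in each arm). At 2.75% missing, imputation is not triggered.
- A mean taken among survivors only would make the effect look about twice as large. In the same case that is (0.08 − 0.03) × 22 = 1.10. The planned analysis is by intention to treat with deaths scored worst, and that roughly halves it.
- A reader might conclude that the outcome cannot see severe impairment at all. Survivors who can be interviewed but score poorly stay in, and incapacity also shows in proxy HRQoL.
- The best-worst and worst-best scenarios are a safeguard against data missing not at random. They are partial, because they depend on imputation being used and set opposite extremes by arm.
- This is one of seven secondary outcomes, tested at the 1% level, with no power claimed.
- Equating an untestable survivor with a death is a choice, and it rests on a reported reason in an open-label trial.

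These points limit the size of the concern. They do not supply the missing rule.

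**Conclusion.** The gap is real. The plan foresees survivors incapable through cognitive impairment or coma, gives them a route for HRQoL only, and leaves their cognitive scores to rules that ignore why the scores are missing. Up to about 10% of survivors could be untestable before imputation or a missing-not-at-random analysis starts, given the planned mortality, deaths counted as observed and no other missing tests.

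Bias in the treatment comparison is possible but not shown. The documents give neither an untestable rate nor a score range, and nothing in them suggests that rates would differ between arms. Equal rates shift the levels and hardly move the difference in means; unequal rates distort it in either direction. The 0.55 versus 0.29 illustration rests wholly on assumed inputs. This is a cheap and worthwhile improvement to a secondary outcome; it does not touch the primary analysis.

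**What to change.** In Protocol Appendix 2 and the SAP:

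1. Record the reason for each missing cognitive test, separating untestable because of coma or cognitive impairment from refusal and from no contact.
2. Give survivors in the first group the worst possible score in both arms, as for non-survivors.
3. Keep the existing missing-data rules for refusal and no contact.
4. Report the cognitive analysis with and without rule 2, whatever the proportion missing.

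The cost is one scoring rule, one field on the 1-year form and one extra analysis. The contact is already planned, because a proxy is approached for HRQoL in these cases. The downside is reliance on a reported reason in an open-label trial; the paired analysis in step 4 shows how much the result depends on it.
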